During the screening period, subjects will be assessed for eligibility to receive study medication. Eligible subjects will apply study medication to the vitiliginous areas of the face and neck and a ½" margin around these areas (excluding upper and lower eyelids [defined as the area from the bony rim of the orbit to and including the eyelids], and mucosal lip area) twice-a-day for up to 48 weeks. If applicable, the subject may treat up to the vermillion border of the mucosal lip and the skin underneath the beard. Assessment of response to treatment will be performed using Canfield 2-D photographic digital image analysis, Facial VASI, Vitiligo Noticeability Scale (VNS), VitiQoL and Subject Vitiligo Satisfaction Scale. These will occur as specified in the Schedule of Assessments. Subjects will be seen at up to 15 study visits, including up to 48 weeks of active treatment followed by a 4-week post-treatment follow-up visit. Subjects who consented for the original study treatment period for up to 28 weeks, and do not consent for the additional visits (Visit 12-15) will complete the study at Visit 11 (Week 28.) Safety and tolerability will be evaluated throughout the study by assessment of electro-cardiograms (ECG), clinical laboratory tests, adverse events including local site reactions, and vital signs.	
Number of Subjects (planned): Approximately 33 subjects will be enrolled.	
Number of Study Sites: This study will be conducted at approximately 5 U.S. clinical sites.	

Inclusion Criteria:

In order to be eligible for the study, a subject must fulfill all of the following criteria:

1. Subject is a male or female \geq 18 years of age.
2. Subject has a clinical diagnosis of new onset or actively progressing non-segmental facial vitiligo or worsening of existing facial lesions within the past 6 months. Actively progressing vitiligo is defined as: subject history of a new vitiliginous lesion or objective signs of disease activity (such as: confetti-like depigmentation, trichrome lesions, and the Koebner phenomenon) as assessed by the investigator. Subjects may have non-facial vitiliginous lesions that are unchanged for more than 6 months provided they meet the requirement for active facial lesions.

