Mean change from baseline in total VASI from baseline (Visit 2) to Week 4, 8, 12, 16, 20 24 and 48 (Visits 5-15) will be assessed for descriptive purposes only to track disease progression in untreated areas.

Safety analyses will include descriptive statistics calculated on the safety parameters using the safety population. The proportion of subjects with treatment-emergent adverse events will be tabulated and presented by treatment and Medical Dictionary for Regulatory Activities (MedDRA) System Organ Class. Vital signs and clinically relevant abnormal laboratory results will also be tabulated and presented. Change from baseline (Visit 2) in the Local Tolerability Assessments (LTA) to end of treatment (Visit 10) will be summarized.

Data from all enrolled and treated subjects will be presented and summarized. Safety summaries will include listings by study medication of adverse events incidences within each MedDRA System Organ Class, and changes from pre-application values in vital signs. Adverse event summaries will be presented showing the proportion of subjects experiencing adverse events, both overall and by MedDRA System Organ Class.

TABLE OF CONTENTS

1. SYNOPSIS	6
2. INTRODUCTION.....	18
2.1. Summary.....	18
3. STUDY RATIONALE.....	20
3.1. Study Rationale.....	20
4. STUDY OBJECTIVES	20
4.1. Primary Objective	20
4.2. Secondary Objectives	20
5. SELECTION AND DISPOSITION OF STUDY POPULATION	20
5.1. Number of Subjects and Study Sites	20
5.2. Study Population Characteristics.....	20
5.3. Inclusion Criteria.....	21
5.4. Exclusion Criteria.....	21
5.5. Previous and Concomitant Medications and Therapies.....	23
5.6. Permitted Concomitant Medications, Therapies and Over the Counter Products (OTC)	23
5.6.1. Prohibited and/ or Restricted Medications	24
5.7. Subject Identifier (SI)	24
5.8. Replacement Subjects	25
5.9. Subject Withdrawal Criteria	25
5.10. Study Termination	25
6. INVESTIGATIONAL PLAN.....	26
6.1. Overall Study Design.....	26
6.2. STUDY PROCEDURES	26
6.3. Schedule of Assessments	27
6.4. Study Visits Description and Procedures	30
6.4.1. Visit 1/ Screening (Day -28 to 0)	30
6.4.2. Visit 2 (Day 1) / Baseline.....	30
6.4.3. Visit 3-9 (Weeks 1, 2, 4, 8, 12, 16 and 20) These visits must occur on the following weeks after Visit 2:	32
6.4.4. Visit 10 (Week 24).....	32
6.4.5. Visit 11 (Week 28).....	33
6.4.6. Visit 12 (Week 32).....	34

6.4.7. Visit 13 (Week 40).....	34
6.4.8. Visit 14 (Week 48).....	35
6.4.9. Visit 15 (Week 52).....	35

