4. STUDY OBJECTIVES

4.1. Primary Objective

The primary objective of this study is to assess the safety, tolerability and efficacy of ATI-50002 Topical Solution, 0.46% in subjects with non-segmental facial vitiligo.

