5.9. Subject Withdrawal Criteria

Subjects will be informed that they are free to withdraw from the study at any time and for any reason. The investigator may remove a subject from the study if, in the investigator's opinion, it is not in the best interest of the subject to continue the study. Examples of other reasons subjects may be discontinued from the study are: a change in compliance with an inclusion or exclusion criterion, occurrence of AEs, occurrence of pregnancy, use of a prohibited therapy or subject is unwilling or refuses to continue with the protocol defined study visits and/or subject withdraws consent (Refer to Section 9.2.4 for study medication discontinuation criteria).

In case of premature discontinuation of study participation, all efforts will be made to perform all Visit 10 (Week 24) assessments or if continuing for the additional 24 weeks, Visit 15 (Week 52). The date the subject is withdrawn from the study and the reason for discontinuation must be recorded in the subject's electronic case report forms (eCRFs). All withdrawn subjects with ongoing AEs will be followed until the event has resolved or stabilized, until the subject is referred to the care of a local health care professional, or until a determination of a cause unrelated to the study medication or study procedures is made.

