6. INVESTIGATIONAL PLAN

6.1. Overall Study Design

This Phase 2, multicenter, open label study is designed to evaluate the safety, tolerability and efficacy of ATI-50002 Topical Solution in subjects with facial non-segmental vitiligo. Subjects will be required to have a clinical diagnosis of new onset or actively progressing non-segmental facial vitiligo involving at least 0.25% TBSA (excluding upper and lower eyelids, mucosal lip areas, beard [if applicable]; and forehead and chin areas covered by the stereotactic positioning device for photography) with at least one area of the face with normal pigmentation. The face is defined as the area from the border of the hairline, not including hair bearing skin to the jawline. Thirty-three subjects will receive ATI-50002 Topical Solution, 0.46%, BID for up to 48 weeks.

During the screening period, subjects will be assessed for eligibility to receive study medication. Eligible subjects will apply study medication to the vitiliginous areas of the face and neck including $\frac{1}{2}$ " margin around these areas (excluding the upper and lower eyelids and mucosal areas of the lips) twice-a-day for up to 48 weeks. Assessment of response to treatment will be performed using the Canfield 2-D Photographic image analysis, Facial VASI, Vitiligo Noticeability Scale, VitiQoL, and Subject Vitiligo Satisfaction Scale. These assessments will occur as specified in the Schedule of Assessments. Subjects will be seen at up to 15 study visits, including up to 48 weeks of active treatment followed by 4 weeks of post treatment follow-up.

Safety and tolerability will be evaluated throughout the study by assessment of electrocardiograms (ECG), clinical laboratory tests, adverse events including local site reactions and vital signs.

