6.4.8. Visit 14 (Week 48)

This visit must occur 48 weeks (\pm 7 days) of Visit 2.

At this visit, the investigator or designee will perform the following procedures:

1. Query the subject in a non-directive manner about any changes in her/his health since the previous visit and report all AEs on the appropriate form.
2. Query the subject about any changes in her/his concomitant therapies since the previous visit and report changes on the appropriate form.
3. Confirm the subject continues to comply with all study restrictions and has followed all study instructions.
4. Measure vital signs.
5. Collect blood samples for clinical laboratory tests.
6. Perform a urine pregnancy test for WOCBP.
7. Perform the F-VASI.
8. Have the subject complete the VNS.
9. Have the subject complete the SVSS.
10. Collect study medication.
11. Have the subject complete the VitiQoL.
12. Take standardized photographs.
13. Review the study instructions with the subject.
14. Schedule the Visit 15 52 weeks \pm 7 days from Visit 14.

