8.2.5. Local Tolerability Assessment (LTA)

The LTA is the investigator's assessment of the average overall severity of signs and the subject's assessment of the average overall severity of symptoms associated with an application site reaction on the treated areas of the face. The investigator and subject must NOT refer to any other evaluation to assist with these assessments. This is not a comparison with the assessment at any other time point.

At Visits 2-11, the investigator and the subject will evaluate the LTA signs and the LTA symptoms respectively.

LTA Signs (Investigator or designee assessment):

- Erythema
- Edema
- Scaling/dryness

LTA symptoms (Subject assessment):

- Stinging
- Burning

The investigator will assess the LTA signs as follows:

- At Visit 2:
 - Prior to the first study medication application
 - 20 (± 4) minutes after the application completion time.
- At Visits 3-11.

The subject will assess the LTA symptoms as follows:

- At Visit 2:
 - Prior to the first study medication application report the LTA for each symptom over the previous 24 hours
 - 10 (± 4) minutes after the application completion time report the average severity since the application completion time.
- At Visits 3-11:
 - Report the average LTA for each symptom over the previous 24 hours.

The investigator, for the signs, should report the one integer that best describes the average overall severity on the treatment areas of the face using the scales below:

Local Tolerability Assessment – Erythema

Grade	Descriptor
0	Clear: No erythema present
1	Mild: Slight erythema
2	Moderate: Definite erythema
3	Severe: Marked, fiery erythema

Local Tolerability Assessment – Edema

Grade	Descriptor
0	Clear: No edema present
1	Mild: Slight edema
2	Moderate: Definite edema
3	Severe: Marked edema

Local Tolerability Assessment – Dryness/Scaling

Grade	Descriptor
0	Clear: No signs of dryness or scaling
1	Mild: Slight roughness (may be more easily felt than seen), barely perceptible scaling
2	Moderate: Moderate roughness, definite scaling
3	Severe: Marked roughness, heavy scaling

The subject, for the symptoms, should report the one integer that best describes the average overall severity on the treatment areas of the face using the scales below:

Local Tolerability Assessment – Itching

Grade	Descriptor
0	Clear: No itching
1	Mild: Slight itching, not bothersome

2	Moderate: Definite itching, slightly bothersome
3	Severe: Intense itching, bothersome and/or uncomfortable

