11.2. Statistical Methods

Summary descriptive statistics (N, mean, median, SD) by visit will be provided for all safety and efficacy parameters. Primary and secondary efficacy parameters are described below:

Primary Efficacy Parameter

Mean change from baseline in facial depigmentation in the AOI will be quantified using Canfield-2-D photographic image analysis from baseline (Visit 2) compared to Week 48 (Visit 14).

Secondary Efficacy Parameters:

Mean change from baseline in facial depigmentation will be calculated as the mean change in Facial assessment of the Vitiligo Area Scoring Index (F-VASI) from Visit 2 compared to Week 24 (Visit 10) and if applicable, Week 48 (Visit 14). F-VASI is a modification of the validated quantitative assessment scale for vitiligo which evaluates the percentage of vitiligo involvement of the face only.

Mean change from baseline in facial depigmentation in the AOI based on Canfield 2-D Photographic analysis from Visit 2 compared to Weeks 4, 8, 12, 16, 20, 24, 32, 40, and post-treatment Week 52 (Visits 5-11, and 12, 13, and 15).

Mean change from baseline in the Facial assessment of the Vitiligo Area Scoring Index (F-VASI) from Visit 2 compared to Weeks 4, 8, 12, 16, 20, 24, 32, 40, 48 and post-treatment Week 52 (Visits 5-11, and Visits 12, 13, 14 and 15).

Mean change from baseline in the VitiQoL from Visit 2 compared to Week 12, 16, 20, 24, and 48 (Visits 7-10, 14).

Treatment success based on the subject's assessment of vitiligo on the Vitiligo Noticeability Scale (VNS) at Week 4, 8, 12, 16, 20, 24, 32, 40, and 48.

Mean change from baseline in total VASI from Visit 2 to Visits 7 and Visit 14 (Week 48) will be assessed for descriptive purposes only to track disease progression in untreated areas.

Safety analyses will include descriptive statistics calculated on the safety parameters using the safety population. The proportion of subjects with treatment-emergent adverse events will be tabulated and presented by Medical Dictionary for Regulatory Activities (MedDRA) System Organ Class. Vital signs and clinically relevant abnormal laboratory results will also be tabulated and presented. Change from baseline in the Local Tolerability Assessments (LTA) to end of treatment (Visit 10) will be summarized.

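### The local tolerability summary calls Visit 10 (Week 24) the end of treatment, but continuing subjects are dosed to Week 48 and have no on-drug tolerability grade after Visit 10

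*Combined protocol and SAP*

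**What the plan says.** Section 11.2 states: "Change from baseline in the Local Tolerability Assessments (LTA) to end of treatment (Visit 10) will be summarized". The Statistical Methods part of the synopsis says the same: "Change from baseline (Visit 2) in the Local Tolerability Assessments (LTA) to end of treatment (Visit 10) will be summarized".

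Section 6.1 describes a longer course, "including up to 48 weeks of active treatment followed by 4 weeks of post treatment follow-up". Under section 6.4.4, Visit 10 falls at Week 24; all drug is collected there and dispensed again only to subjects who agree to continue. Those subjects carry on to Visit 14 at Week 48, where section 6.4.8 has the site "Collect study medication". By the synopsis, subjects who decline the extension finish at Visit 11 (Week 28), so for them Visit 10 is the true end of dosing.

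Section 8.2.5 fixes the grading visits: "At Visits 2-11, the investigator and the subject will evaluate the LTA signs and the LTA symptoms respectively". The Visit 12-15 table in section 6.3 has no LTA row, and the procedure lists in sections 6.4.6 to 6.4.9 have no LTA step.

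For premature discontinuation, section 5.9 asks the site to "perform all Visit 10 (Week 24) assessments or if continuing for the additional 24 weeks, Visit 15 (Week 52").

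**The concern.** Tolerability is named in the primary objective (section 4.1), and the LTA is the only scale in the plan that grades named local signs and symptoms from 0 to 3. The wording of its summary fits a 24-week course. With treatment now running to Week 48, two things go wrong for continuing subjects.

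First, a mid-course grade is labelled as the end-of-treatment grade. Suppose a continuing subject stops at Week 30 because of a local reaction. The LTA summary would show that subject's Week 24 grade, from before the reaction. The adverse event tables would count the event, but the LTA result would not reflect it.

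Second, the label cannot be corrected at analysis, because no later on-drug grade is collected. The by-visit safety summaries that section 11.2 also promises will have no on-drug LTA after Week 24.

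The timing adds to this. Section 5.6 allows narrowband UVB once Visit 9 is complete. Erythema and burning are LTA items, yet only one scheduled on-drug LTA can reflect combined use.

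**Working it through.** The plan gives no power or sample-size figure on this point, so the check compares the schedule tables and procedure lists and counts days.

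**Inputs: scheduled treatment days (section 6.3)**

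| Visit | 2 | 3 | 4 | 5 | 6 | 7 | 8 | 9 | 10 | 11 | 12 | 13 | 14 |
|---|---|---|---|---|---|---|---|---|---|---|---|---|---|
| Day | 1 | 8 | 15 | 29 | 57 | 85 | 113 | 141 | 169 | 197 | 225 | 281 | 337 |
| LTA scheduled | yes | yes | yes | yes | yes | yes | yes | yes | yes | yes | no | no | no |

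**Step 1. Does Visit 11 fill the gap?** Section 6.4.5 says Visit 11 is marked as not done for subjects who agree at Visit 10 to continue. Subjects who consent at Visit 11 handed in all drug at Visit 10, nominally 197 - 169 = 28 days earlier. The symptom part of the LTA covers the previous 24 hours (section 8.2.5), so their Visit 11 grade is an off-drug grade. Visit 11 supplies no on-drug LTA in either case.

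**Step 2. Does the early-stop rule fill it?** A subject who stops before Week 24 has the Visit 10 assessments, which include both LTAs (section 6.4.4). A subject who stops in the extension has the Visit 15 assessments, and the list in section 6.4.9 contains no LTA. The rule covers the first half of treatment only.

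**Step 3. Grading interval up to Week 24.** Successive differences from Visit 2 to Visit 10 are 7, 7, 14, 28, 28, 28, 28 and 28 days. They sum to 168, and the longest is 28.

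**Step 4. Time on drug after the last on-drug LTA.**
- Full course: 337 - 1 = 336 days. After Visit 10: 337 - 169 = 168 days. Share: 168/336 = 50%.
- Restart at Visit 11: 337 - 197 = 140 days. Total on drug: 168 + 140 = 308 days. Share: 140/308 = 45%.

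**Step 5. Visits affected.** Post-baseline on-drug visits with LTA are Visits 3-10, which is 8. Those without are Visits 12, 13 and 14, which is 3. Share without: 3/11 = 27%.

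**Step 6. Overlap with narrowband UVB.** On-drug visits after Visit 9 are Visits 10, 12, 13 and 14. Of these four, only Visit 10 has an LTA.

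**Step 7. With LTA added at Visits 12-14.** For a full course the intervals after Visit 10 become 225 - 169 = 56, 281 - 225 = 56 and 337 - 281 = 56 days, in place of 168 ungraded days.

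**The case against.** The strongest reply concerns weight. This is a descriptive, single-arm pilot, and no test or decision uses the LTA. The sentence names its visit, so an analyst would correctly compute the Week 24 change, which is also the time of the planned initial analysis. The lists of safety and tolerability measures in the synopsis and section 6.1 name adverse events including local site reactions, not the LTA, and adverse events are collected through Visit 15. Application-site events also lead to documented dose changes (section 7.6), related events are followed until resolved or stable (section 9.2.1), and Visit 15 includes a skin examination. The omission of the LTA after Visit 11 is consistent across the schedule and procedure lists. The extension is lighter elsewhere too, with no ECG at Visits 12-14, so the omission may be deliberate. Extra grades could not separate a drug effect from a UVB effect.

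Much of this stands. No number would be miscalculated, local reactions would not go unrecorded, and the design could not attribute a late reaction to either treatment. These points limit the severity.

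They do not remove the problem. The label is wrong for continuing subjects whether or not the lighter schedule was intended. Adverse events are elicited by a non-directive question about changes in health (section 9.2.1), whereas the LTA asks for a grade on each named item, including mild symptoms that do not bother the subject. Section 11.2 tabulates adverse events overall and by System Organ Class; it specifies no severity table and no breakdown for Weeks 24-48. For a subject who completes the course, the Visit 15 skin examination comes four weeks after dosing ends. The protocol places the LTA under Assessment of Safety, and section 11.2 picks it out by name for a change-from-baseline summary.

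**Conclusion.** The concern holds. In both places the end-of-treatment label is correct only for subjects who do not enter the extension. For those who do, the plan would present a grade from halfway through a full course as the final one, with no on-drug LTA in the remaining 168 days (140 days after a Visit 11 restart).

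The figures assume scheduled visit days and dosing through Visit 14. They apply to continuing subjects only, and that number could be anywhere from 0 to 33; at 0 the label would be right. The number using narrowband UVB is also not given. This should be corrected, but it does not threaten the efficacy analysis or the conduct of the trial.

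**What to change.** 1. In section 11.2 and the synopsis, replace the end-of-treatment label on Visit 10 with Week 24.
2. Add the existing investigator and subject LTA at Visits 12, 13 and 14, and at an early-stop visit in the extension. Update sections 5.9, 6.3, 6.4.6 to 6.4.8 and 8.2.5 to match.
3. Summarise change from baseline at Week 24 and at each subject's last on-drug visit. Where drug had already stopped before an early-stop visit, report that grade separately.
4. If those visits have passed, state in the report that LTA was graded to Week 24 only, and tabulate application-site adverse events in Weeks 24-48 by severity.

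Items 1 to 3 need a small amendment with IRB approval and add one brief, familiar grading at three existing visits and at early stops. Item 4 needs only the wording change and one adverse event breakdown. Treatment, the efficacy analysis and the sample size do not change.

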12. TRAINING, MONITORING, DATA MANAGEMENT AND QUALITY ASSURANCE

12.1. Training

For each investigational center, there will be an initiation visit prior to enrolling any study subjects.

It is strongly recommended that all investigators, other evaluators, study nurses, study coordinators or other applicable personnel attend this visit. During this visit, participants will be trained to the protocol, study specific procedures, and the eCRFs. Those unable to attend the initiation visit must receive on-site training from an appropriately trained individual prior to participating in any of the procedures and evaluations in this study.

Clinical Research Associates (CRAs) and other applicable personnel will be trained prior to study initiation to familiarize CRAs with the disease, the Standard Operating Procedures (SOPs), the protocol and other study specific items. Team organization, communication and operational issues will also be discussed.

Aclaris Therapeutics, Inc. will provide an investigational center file to each center.

12.2. Monitoring

The conduct of the study will be closely monitored by representatives of Aclaris Therapeutics, Inc. to verify adherence to ICH Good Clinical Practice (GCP) guidelines, and applicable SOPs. Reports of these verifications will be archived with the study report. The investigator will allow the Aclaris Therapeutics, Inc. representative's designee and/or any regulatory agency to have direct access to all study records, eCRFs, corresponding subject medical records, study medication-dispensing records and study medication storage area, and any other documents considered source documentation. The investigator also agrees to assist the representative, if required.

